**Table 1. Outcomes by Protocol and Aim**

Protocol 1			
Outcomes	Aim 1	Aim 2	Aim 3
Primary	Clinic systolic and diastolic pressures; Ambulatory systolic and diastolic pressures	Pulse Wave Velocity (measure of arterial stiffness)	Acute and chronic pressure reductions
Secondary	Heart rate; Cardiac output; Stroke volume; Total peripheral resistance; Secondary BP outcomes: waking, sleeping, dipper vs. non-dipper	Blood-borne biomarkers	
Protocol 2			
	Cognitive	Brain biomarkers of ADRD risk	
Primary Outcomes	Memory domain composite score*	Arterial transit time: mean perfusion in gray matter, mean perfusion in white matter	

\*average of age-corrected list-sorting and age-corrected picture sequence z-scores

## 5 Study Methods

### 5.1 General Study Design and Plan

We will address our aims in a randomized clinical trial comparing the effects of heat therapy versus aerobic exercise training. This is a well-controlled, clinically relevant approach, as we will be comparing our novel heat therapy intervention directly to the current idealized standard of care, an aerobic-exercise intervention. We will specifically study individuals with Elevated or Stage 1 HTN, in the absence of cardiovascular events such as heart attacks or strokes, diabetes, or chronic kidney disease, as current guidelines do not mandate prescribing medications to these individuals. They are the ideal target group for the proposed intervention, as it has the potential to obviate the need for life-long pharmacological therapy. The table at the right depicts the workflow for this clinical trial protocol, which is as follows:

**RECRUIT:** The trial will be conducted in a cohort of physically inactive to moderately active men and women with high blood pressure (Elevated and Stage 1 or 2 Hypertension, based on current guidelines) from the local Eugene and Springfield, OR communities (details under section D). Potential subjects will be pre-screened by phone to determine eligibility.

**PRE-SCREEN:** Candidates will complete a pre-screening consent and answer pre-screening questions online and over the phone. If candidates appear to qualify, they will be further screened for eligibility over the phone using the IPAQ.

**SCREEN:** Subjects will need to come to the laboratory on two separate occasions as part of the initial screening process. Seated blood pressure will be measured on two separate screening visits to determine resting blood pressure. During each visit, blood pressure

will be measured twice, performed according to clinical guidelines for assessing hypertension. The average blood pressure of these four readings obtained over two assessments must fall within the inclusion criteria range to qualify for inclusion in the study. If the average blood pressure of these four readings (two obtained during Screening Day 1 and two obtained during Screening Day 2) does not fall within the allowable limits for this study, the subject will be excluded from the study. During Screening Day 1, the informed

consent process will be completed for Protocol 1. We will also assess medical history, BMI, fasting glucose, hemoglobin A1c, and lipid profile to verify eligibility. If the subject is interested in participating in Protocol 2, the informed consent process for

**PRE-TESTS:** Before and after the **INTERVENTION**, we will conduct high-resolution phenotyping of subjects which will include: lab-based hemodynamic tests of vascular function; blood-based biomarkers related to cardiovascular health; 24-h urine collection; 24-h food/beverage log; 24-h ambulatory blood pressure recording; VO2peak fitness test. These are detailed below *Specific Experimental Approaches*. **ASSIGN:** Subjects will be randomized to either the heat therapy group or exercise training group, then undergo 30 sessions of the

specific intervention at a rate of 3-4 per week over an 8 to 10-week period. Randomization will be stratified by age and sex to ensure equal numbers within each stratum. Further stratification, for example by BMI or initial blood pressure, would be difficult given the small sample size. (More details of the randomization process are under *Randomization*). After the first 15 sessions, subjects will be re-tested for hemodynamic and biomarker adaptations to the intervention (INTERIM-TEST). After 30 sessions, subjects will undergo final POST-TESTS.

**INTERVENTION:** Subjects in the **heat therapy** group will report to the lab to undergo heat therapy sessions 3-4 times per week, with 45 minutes of hot water immersion per session. The goal of heat therapy is to maintain core temperature above 38.5°C for at least 30 min. This target has previously been shown to be the threshold temperature and time exposure to optimize adaptations to passive heat exposure. Subjects in our lab, including sedentary, hypertensive, obese, and spinal cordinjured subjects, have tolerated this heating protocol very well. Subjects will be checked for euhydration prior to entering the tub and will be monitored closely throughout heating for heart rate and blood pressure during all sessions. In addition, core temperature (Tcore; FDA approved ingestible core temp sensing pill; Accutemp Temperature Monitoring System by HQ Inc.) will be monitored during the first 5 and final sessions whereas aural temperature may be monitored in all sessions. Subjects will be removed from the hot bath if Tcore exceeds 39.5°C. Water immersion is the preferred method of heating since it is capable of increasing core temperature and heart rate at a rate similar to moderate-intensity exercise. Subjects in the **exercise training** group will report to the lab for a supervised exercise training session 3-4 times per week. We will use heart rate responses determined during baseline VO2 peak testing to assign workloads during each session. Exercise will consist of a 5-minute warm-up of seated upright cycling at 30% of the subject's VO2 peak, followed by 40 minutes of cycling at 60% VO2 peak, then a 5-minute cool down at 30%. In addition, core temperature will be monitored during the first and final sessions. On the 1st heat therapy or exercise training session, the subject will lay supine for 20 min of rest followed by three measures of blood pressure before the heat therapy or

**Figure 1. Study Time Points**

RECRUIT
- Inactive men and women with HTN
SCREEN
- Multiple visits to assess blood pressure
PRE-TESTS
- Hemodynamic tests
- Muscle sympathetic nerve activity
- Biomarkers
- 24-h Ambulatory blood pressure
- VO 2 Peak Test
- Heat Test
ASSIGN
- Randomized to intervention group
INTERVENTION
- First 15 sessions
INTERIM-TESTS
- Hemodynamic tests
- 24-h Ambulatory blood pressure
- Biomarkers
INTERVENTION
- Last 15 sessions
POST-TESTS
- Hemodynamic tests
- Muscle sympathetic nerve activity
- Biomarkers
- 24-h Ambulatory blood pressure
- VO 2 Peak Test
- Heat Test

exercise training session. At the end of this 1st session, the subject will lay down for 1 hour of recovery, during which, we will continue to monitor core temperature, heart rate, and blood pressure every 5 min. NOTE: Subjects with contraindications for the ingestible core temp sensing pill will be encouraged to use a self-inserted rectal thermistor. If subject is contraindicated for the core temp pill and the rectal thermistor, their temperature will be monitored with a digital aural or oral thermometer.

**INTERIM-TESTS:** After half the intervention sessions have been completed, we will repeat our assessment of hemodynamic tests, 24-h urine collection and food/beverage log, 24-h ambulatory blood pressure and sleep/wake/activity log, and blood-based biomarkers related to cardiovascular health.

**POST-TESTS:** After the INTERVENTION, we will repeat high-resolution phenotyping of subjects which will include all the measures from the PRE-TESTS.

## 5.2 Inclusion-Exclusion Criteria and General Study Population

**INCLUSION CRITERIA:** Systolic pressure  $\geq 120$  and  $< 140$  mmHg or diastolic pressure  $\geq 80$  and  $< 90$  mmHg; ages  $\geq 35$  and  $< 60$ . Protocol 2 will be completed on Screening Day 2 and the subject will be pre-screened using the MRI PRE-SCREENING FORM, LCNI MRI SAFETY SCREENING QUESTIONNAIRE and MMSE. Subjects who undergo screening and satisfy all inclusion criteria and no exclusion criteria will be enrolled in the study and progress to a battery of pre-intervention tests (PRE-TESTS).

**EXCLUSION CRITERIA:** Secondary hypertension and/or target-organ damage; CVD other than hypertension; Abnormal resting or exercise ECG; Currently on antihypertensive drugs; Obesity Class 2 or greater (BMI  $\geq 35$ ); fasting glucose  $\geq 126$ ; hemoglobin A1c  $\geq 7\%$ ; LDL  $\geq 160$  mg/dL; Participation in aerobic exercise  $\geq 30$  min/session and  $\geq 1$  sessions/week, based on self-reported exercise habits over the prior 12 months; Women who are pregnant, nursing, or desiring to become pregnant.

## 5.3 Randomization and Blinding

**Randomization.** As indicated above, subjects will be randomized to either the heat therapy group or exercise training group. While subjects will not be blind to their treatment group, preliminary analysis of data and data entry will be by a blinded researcher (i.e., this will be a partially blind/observer-blind trial). The randomization and blinding process will be coordinated by [name] (a biostatistician at OHSU who is supporting this project). In brief, the Research Coordinator will enter age, sex, and subject ID number into a web-enabled randomization database via REDCap and receive the randomized group assignment. As indicated above, randomization will be stratified by age and sex to ensure equal numbers within each stratum. Further stratification, for example by BMI or initial blood pressure, would be difficult given the small sample size.

## 5.4 Study Assessments

Timing and frequency of study assessments are shown in **Figure 1**. Descriptions of outcome variables collected are shown below in **Table 3**. See **Derived Variables** section below for additional calculated outcomes.

**Table 3. Non-derived variables used in study assessments**

Variable	Aim/Primary or Secondary	Description
Protocol 1		
syst_bp_mean	Aim 1/Primary	Continuous; average of 3 systolic BP measurements collected in clinic at pre-, interim-, and post-intervention timepoints
diast_bp_mean	Aim 1/Primary	Clinic diastolic BP; Continuous; average of 3 diastolic BP measurements at 2 screening

		visits collected in clinic at pre-, interim-, and post-intervention timepoints
mean_rest_hr	Aim 1/Secondary	Continuous; average of 3 resting heart rate measurements collected in clinic at pre-, interim-, and post-intervention timepoints
Mean_qc	Aim 1/Secondary	Continuous; average of 3 cardiac output measurements collected in clinic at pre-, interim-, and post-intervention timepoints
Mean_qc	Aim 1/Secondary	Continuous; average of 3 cardiac output measurements collected in clinic at pre-, interim-, and post-intervention timepoints
Protocol 2		
mean_pcalib_gm	Brain biomarkers of ADRD/primary	Continuous; Mean perfusion calibration in gray matter, measure of arterial transit time
mean_pcalib_wm	Brain biomarkers of ADRD/primary	Continuous; Mean perfusion calibration in white matter measured by MRI, measure of arterial transit time

Note: means calculated in REDCap are not considered derived variables for the purposes of this table.

## 5.5 Derived variables

For ambulatory blood pressure measures, subjects self-report waking and sleeping hours. The BP assessment interval for waking hours is every 20 minutes, compared to every 60 minutes during sleeping hours. For 24H ambulatory BP, day and night readings were weighted to account for the higher number of daytime readings.

**Table 4. Derived variables used in study assessments**

Derived Variable	Aim/Primary or Secondary	Description
Protocol 1		
abp_syst	Aim 1/Primary	Continuous; weighted average 24H ambulatory systolic BP
abp_dyas	Aim 1/Primary	Continuous; weighted average 24H ambulatory diastolic BP
abp_day_syst	Aim 1/Secondary	Continuous; average day ambulatory systolic BP
abp_night_syst	Aim 1/Secondary	Continuous; average night ambulatory systolic BP
abp_day_dyas	Aim 1/Secondary	Continuous; average day ambulatory diastolic BP
abp_night_dyas	Aim 1/Secondary	Continuous; average night ambulatory diastolic BP
sv	Aim 1/Secondary	Continuous; stroke volume is calculated as mean_qc*1000/ mean_qc_hr rounded to 3 decimal places
tpr	Aim 1/Secondary	Continuous; total peripheral resistance is calculated as mean_map/mean_qc rounded to 3 decimal places, where mean_map is mean arterial pressure
sbp_dipper	Aim 1/Secondary	Categorical; non-dipper <10%, dipper ≥10% to <20%, and extreme dipper ≥20% change in systolic BP at night calculated from ambulatory BP day and night averages

**HEAT THERAPY VS EXERCISE TRAINING IN HYPERTENSION SAP**

dbp_dipper	Aim 1/Secondary	Categorical; non-dipper <10%, dipper ≥10% to <20%, and extreme dipper ≥20% change in diastolic BP at night calculated from ambulatory BP day and night averages
pwv	Aim 2/Primary	Continuous; average of three pulse wave velocity measurements collected at pre-, interim-, and post-intervention timepoints
il6_lg2	Aim 2/Secondary	Continuous; Biomarker IL-6 with the lower limit of detection (LLD) of 0.031 imputed for <LLD, log2 transformed for normalcy
crp_lg2	Aim 2/Secondary	Continuous; Biomarker CRP with the lower limit of detection (LLD) of 0.031 and upper LD (ULD) of 50 imputed for <LLD and >ULD, log2 transformed for normalcy
et1_lg2	Aim 2/Secondary	Continuous; Biomarker ET-1 with the lower limit of detection (LLD) of 0.031 imputed for <LLD, log2 transformed for normalcy
alb_lg2	Aim 2/Secondary	Continuous; Biomarker urine albumin with the lower limit of detection (LLD) of 0.031 imputed for <LLD, log2 transformed for normalcy
Supine.SBP.low	Aim 3/Primary	Continuous; average of three lowest consecutive supine systolic blood pressure measurements taken every 5 minutes for an hour post-intervention during supine recovery (for Heat Therapy: syst_bp55_ht_s1 to syst_bp110_ht_s1; for Exercise Training: for Heat Therapy: syst_bp55_ex_s1 to syst_bp110_ex_s1)
Supine.DBP.low	Aim 3/Primary	Continuous; average of three lowest consecutive supine systolic blood pressure measurements taken every 5 minutes for an hour post-intervention during supine recovery (for Heat Therapy: syst_bp55_ht_s1 to syst_bp110_ht_s1; for Exercise Training: for Heat Therapy: diast_bp55_ex_s1 to diast_bp110_ex_s1)
Supine.SBP.1.ch	Aim 3/Primary	Change from average pre-session resting SBP to Supine.SBP.low
Supine.DBP.1.ch	Aim 3/Primary	Change from average pre-session resting DBP to Supine.SBP.low
eGFR	Aim 1/Exploratory	eGFR was calculated using the CKD-EPI Creatinine-Cystatin Equation (2021) using the CKDEpi_RF.creat.cys function in the nephron R package and rounded to two decimal places
uacr	Aim 1/Exploratory	Urine albumin creatinine ratio (mg/g) was calculated by dividing urine albumin by urine creatinine/1000 rounded to 2 decimal places
Protocol 2		
cognitive_score	cognitive/Primary	Averaged z-scores (centered & divided by standard deviation) of age-corrected picture sequence score (age_cor_score)

		and age-corrected list-sorting score (list_age_cor_scpre)
--	--	--

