Arterial stiffness indices. We will measure **pulse wave velocity**, as done previously⁷. Tonometry pressure tracings will be obtained from the common carotid and ipsilateral common femoral artery (all recordings will be performed on the left side of the body). Time delays between pressure tracings will be calculated using the upswing of the pressure tracing²².

Pulse wave velocity²³ will be calculated as the direct distance between the probe and the thigh cuff divided by the time delay.

Biomarkers. Methodology for blood-based biomarkers is well-established in our research program. All venous blood samples will be collected into appropriate vacutainers, centrifuged, and serum/plasma separated. For purpose of screening, hemoglobin A1C, glucose, and lipids will be analyzed immediately in the investigator's lab (Afinion II, Cholestech LDX). All other samples will be stored at -80°C until delivery by courier to the Oregon Clinical and Translational Research Institute (OCTRI) at Oregon Health and Science University. OCTRI will analyze samples for fasted glucose and insulin (for the calculation of the homeostatic model assessment of insulin resistance (HOMA-IR). Samples collected for measurement of circulating biomarkers of cardiovascular health (IL-6, C-reactive protein, oxidized LDL, ET-1) and renal function (angiotensin II, plasma renin activity, aldosterone) will also be measured at OCTRI. A reduction in oxidized LDL will indicate reduced oxidative stress. Reduced C-reactive protein will indicate reduced systemic and vascular inflammation. HOMA-IR will be calculated using the available on-line calculator from the Oxford Center for Diabetes. Three 40mL blood draws will occur throughout the study immediately following the last void of the 24-hour urine collection during the Pre, Interim, and Post Tests.

24-hour Urine Collection. 24-hour urine collections are the gold standard for measuring basal kidney function (i.e., creatinine clearance, urinary albumin excretion, urinary sodium excretion). Subjects will be given two urine collection containers to take home. In our experience, subjects typically only need to use one container in a 24-hour period. Therefore, the second collection

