container serves as a backup if needed. Additionally, subjects will be offered a specimen container pan to assist in collecting urine samples. Subjects will be instructed to completely void their bladder immediately prior to starting the 24-hour urine collection, after which they will be instructed that all subsequent urine voids are collected in the provided containers. Upon completion of the 24-hour collection, subject will return the urine collection containers to the lab where sample volume and specific gravity will be measured. A blood sample will be collected immediately following the last void of the 24-hour urine collection. Urine samples will be analyzed at a later time for osmolality and urine biomarkers.

Food/Beverage Log. We are not specifically controlling the subjects' dietary patterns with the exception of asking them to abstain from caffeine for 12 hours and alcohol for 24 hours prior to the start of the VASCULAR STUDY visits. However, because of the importance of sodium intake and kidney function, subjects will be instructed to document their food and beverage intakes for the 24-hours immediately preceding the pre-, interim-, and post-VASCULAR STUDY visits. These logs will be analyzed to determine total intakes for energy (kilocalories), fat, protein, carbohydrate, sugar, dietary fiber, sodium, caffeine, and fluid volume. Pre-, interim-, and post-VASCULAR STUDY intakes will be used to compare changes in 24-hour kidney function.

24-h Ambulatory Blood Pressure. Subjects will wear an ambulatory blood pressure monitor for 24 hours. Ambulatory pressure will be monitored using a commercially available unit set to record pressure every 20 minutes during the daytime and every hour at night. This provides a means to study the "real world" impact of chronic exercise on arterial pressure and may be a better predictor of cardiovascular morbidity and mortality. Studies have shown that the prognostic significance of ambulatory blood pressure is in general superior to that of office blood pressure in healthy populations as well as in untreated and treated hypertensive individuals^{10,11}. Subjects will be given a set of instructions and also be asked to complete an activity log during ambulatory blood pressure monitoring and record activities performed during each hour of the day, any unusual physical or emotional events, and sleep and wake times. This deidentified activity log will be returned to the investigator.

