VO₂ Peak Test. Exercise testing is well-established in our research program^{9,12,13}. Subjects will have their peak aerobic power (VO₂Peak) and maximal heart rate determined with a graded maximal cycle ergometer test. This test will be used to assess changes in aerobic fitness in both groups and will be used to determine exercise prescriptions for the aerobic exercise training sessions. VO₂ will be measured using a mixing chamber and mass spectrometer with subjects on an electromagnetically braked cycle ergometer. Heart rate will be measured by a Polar Heart Rate Monitor.

Heat Therapy. Passive heating is well-established in our research program^{7,14}. For Heat Therapy sessions (Heat Therapy group only), subjects will be immersed in hot water for up to 45 mins on 30 occasions. On each day a subject will undergo Heat Therapy, we will obtain a urine sample first to determine whether the subject is dehydrated (determined by urine specific gravity reading >1.024). We will also measure nude body weight before and after the heat exposure. When possible, this will be performed by lab personnel of the same sex as the subject. The scale will be inside a restroom with the readout on the outside of the restroom to maximize subject privacy and comfort. During the first five and final session of Heat Therapy for each subject, core temperature will be continuously monitored and recorded using a wireless, disposable core temperature sensing pill. After the first 5 sessions, once an individual subject's sensitivity to heating has been established, subsequent sessions may be monitored with an infrared aural temperature monitor. There are some risks associated with heat exposure, including: fatigue, light-headedness, muscle cramps, dehydration, and neurological detriments (i.e., heat stroke). However, these symptoms do not typically occur until core temperature rises above 40°C. Subjects will be removed from the hot bath immediately if either core temperature reaches 39.5°C or the subjects experience any symptoms of heat-related illness. All symptoms subside upon lowering core temperature. Ice packs will be on hand if rapid cooling is necessary. Heart rate will also be continuously monitored and recorded throughout heating. If heart rate increases >60 beats/min above resting or increases >20 beats/min with a 5-min time period,

subjects will be moved to a seated position if they were previously fully submerged or removed from the hot tub if they were already sitting up.

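### The Aim 2 secondary outcome for urine albumin is not normalised to the measured 24 h volume or to creatinine, so a between-arm difference in urine volume could appear as an albumin effect

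*SAP*

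**What the plan says.** Protocol section C (24-hour Urine Collection) gives the reason for the collection: "24-hour urine collections are the gold standard for measuring basal kidney function (i.e., creatinine clearance, urinary albumin excretion, urinary sodium excretion". When the containers come back, "sample volume and specific gravity will be measured". Collections are made before, midway through and after the intervention, in both arms.

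SAP section 5.5, Table 4, lists alb_lg2 as Aim 2/Secondary: "Continuous; Biomarker urine albumin with the lower limit of detection (LLD) of 0.031 imputed for <LLD, log2 transformed for normalcy". The row has no volume term, no creatinine term and no units. The same table defines a dilution-adjusted measure, uacr: "Urine albumin creatinine ratio (mg/g) was calculated by dividing urine albumin by urine creatinine/1000 rounded to 2 decimal places". That row is labelled Aim 1/Exploratory, and the only analyses that name it are the correlations and principal component analysis in SAP section 9.1.

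SAP section 9 tests Aim 2 through the interaction of intervention group and timepoint. SAP section 4.2, Table 1, describes the Aim 2 secondary outcomes as blood-borne biomarkers, a label that does not cover a urine measure.

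On hydration, Protocol section C (Heat Therapy) says that on each heat day "we will obtain a urine sample first to determine whether the subject is dehydrated". The Exercise Training text has no such step. The Food/Beverage Log text applies to all subjects at all three test points and includes fluid volume among the intakes analysed.

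**The concern.** The quantity that the SAP analyses is not the one that the protocol names. Excretion is an amount per 24 hours. Albumin concentration also depends on how much water the kidney passed that day. The multiplier that turns one into the other is collected but does not enter the outcome.

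Two consequences follow. Day-to-day variation in urine volume adds noise to the outcome in both arms. In addition, if the interventions changed urine volume differently, the difference would be read as an albumin effect with no change in the kidney. SAP section 7.5 applies no control for multiple comparisons, so a spurious result would meet no further hurdle.

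**Working it through.** The documents give no effect size, SD or power for urine albumin, so there is no planned figure to reproduce. The check is of the definition and of how volume passes through it.

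**Is alb_lg2 a concentration?** Table 4 does not say. A detection limit belongs to an assay reading, and no row of Table 4 multiplies anything by volume. The uacr formula divides the same albumin variable by creatinine to reach mg/g. That fits two concentrations, although two 24 h totals would also give mg/g. Concentration is therefore a strong inference and not a stated fact.

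**Effect of dilution.** Concentration = excretion / volume. With excretion constant, the shift in log2 concentration is -log2(V_post / V_pre). The documents give no volumes, so these ratios are assumptions:

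- x1.10: -0.138 log2 (9.1% lower)
- x1.25: -0.322 log2 (20.0% lower)
- x1.50: -0.585 log2 (33.3% lower)
- x2.0: -1.000 log2 (50.0% lower)

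**Effect on the Aim 2 test.** Bias in the interaction = -[log2(volume ratio, heat) - log2(volume ratio, exercise)]. Under assumed ratios:

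- heat x1.25, exercise x1.25: 0
- heat x1.25, exercise x1.0: -0.322 (ratio 0.80)
- heat x1.5, exercise x1.25: -0.263 (ratio 0.83)
- heat x1.5, exercise x1.0: -0.585 (ratio 0.67)

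Exchanging the arms reverses the sign.

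**Effect on the alternatives.** Assume excretion of 10 mg/24 h, creatinine of 1500 mg/24 h, and volumes of 1.5, 2.0 and 2.5 L. Concentration goes 6.67, 5.00, 4.00 mg/L (log2: 2.737, 2.322, 2.000). Excretion stays at 10 mg/24 h, and albumin/creatinine stays at 10 / 1.5 = 6.67 mg/g. Neither moves under pure dilution.

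**Noise without any imbalance.** Assume a within-person volume CV of 15% to 35%, log-normal and independent between visits. The SD on the log2 scale is sqrt(ln(1 + CV²)) / ln 2 = 0.215 to 0.490. The SD of a pre-post change is sqrt(2) times that, 0.30 to 0.69. The protocol needs 40 completers, so about 20 per arm at 50:50. Volume alone then contributes a standard error of SD x sqrt(2/20) = 0.10 to 0.22 log2 to the arm difference.

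**Detection limit (query only).** Table 4 gives 0.031 for IL-6, CRP, ET-1 and urine albumin. The fill-in sits at log2(0.031) = -5.01. If an assay's true limit were 10 or 100 times higher (assumption), each filled value would be log2(10) = 3.32 or log2(100) = 6.64 units too low.

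**The case against.** A reader might infer that fluid intake is monitored in the heat arm only, and so that the heat arm will show a false fall in albumin. The documents do not support this. Fluid intake is logged in both arms at all three test points, and the protocol intends those logs for comparing changes in 24 h kidney function. Only the session-day specific-gravity check is confined to heat. It is a screen for dehydration, and the text does not say what follows a failed reading. The urine collection is a separate at-home period. The visit table lists it together with ambulatory blood pressure monitoring, during which exercise and heat are barred for everyone (General Methodological Considerations). Volume changes shared by both arms cancel in the interaction.

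A reader might also infer that the common value 0.031 is an error. The documents give no units, assay limits or counts of censored samples, so this can only be asked.

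It is fair, too, that urine albumin is peripheral. No hypothesis or listed output names it, no primary outcome is affected, the study describes itself as hypothesis-generating, and uacr is already derived.

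These points limit the size of the concern but do not remove it. The fluid log is not a term in any analysis of alb_lg2, and the adjusted measure ranks below the unadjusted one, under a different aim.

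**Conclusion.** The definition should change. As written, alb_lg2 departs from the quantity that the protocol names, although the data needed to obtain that quantity are collected. Volume differences add noise, and a between-arm difference in volume change could appear as an albumin effect: -0.32 log2 in the assumed case of x1.25 against x1.0, and 0 when both arms change alike. This rests on alb_lg2 being a concentration; if the variable already held a 24 h amount, the concern would fall away and only the missing units would need mending. Whether an imbalance exists, how large it is and which arm it favours are not established. The detection limit is a question for the laboratory and not a finding.

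**What to change.** - Define the secondary albumin outcome as log2 of 24 h albumin excretion (concentration x 24 h volume), or as log2 albumin/creatinine ratio, and state the units.
- Check that collections are complete with total 24 h creatinine. The albumin/creatinine ratio cannot do this, because a missed void removes both parts together.
- Keep raw log2 concentration as a supportive analysis.
- Bring the Table 1 label for Aim 2 secondary outcomes into line with the urine measure in Table 4.
- As a query, ask the laboratory to confirm that 0.031 is the detection limit, in its own units, for each of IL-6, CRP, ET-1 and urine albumin. Correct any row where it is not.

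The cost is SAP wording and a re-derivation from measurements already planned. There are two small downsides. Excretion depends on complete collection. The redefinition also comes late: SAP sections 8.2 and 13 show that data had been examined when those parts were written. The change should therefore be recorded as an SAP amendment with its timing relative to data inspection disclosed.
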